The presence of pain, and in particular joint pain, can significantly interfere with mobility, and an impaired physical performance can eventually affect the cognitive performance.¹⁴ The Self-Administered Patient Satisfaction (SAPS) Scale is used as a more comprehensive measure of patient recovery after surgery, since it includes the overall satisfaction with surgery, self-reported extent of pain relief, and ability to perform home or yard work, and recreational activities.¹⁵ Therefore it is also plausible to hypothesize an association of patient satisfaction (as measured by the SAPS) after surgery with long-term cognitive changes (**objective 1**).

Mechanisms with which postoperative pain and satisfaction could affect postoperative cognitive changes are unclear. One interesting hypothesis is that pain and satisfaction might interact with cognitive abilities through neurogenesis interference (**objective 2.a**).⁸ This would be similar to what is observed in depression.^{16,17} Numerous studies in animals have linked depression with hippocampal-reduced neurogenesis. In rodents, reduced neurogenesis is both a consequence of chronic stress exposure, and a vulnerability that predisposes animals to develop depressive symptoms when later subjected to stress.¹⁸ In the absence of a non-invasive measure of neurogenesis in humans, correlational evidence in human studies has identified several high interference memory tests (like the Mnemonic Similarity Test [MST]) as putatively neurogenesis-sensitive, because they are similarly impacted by factors that alter neurogenesis levels in rodents.^{19,20} In humans, deficits on the MST are associated with elevated scores on scales of

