stress, depression and binge drinking, and with increased age, while several weeks of high intensity exercise improve MST scores.^{21 22} Even if 30% of the NeuroVISION participants presented a decline of ≥ 2 points in their Montreal Cognitive Assessment (MoCA) score at 1 year, many participants experienced no changes or an improvement in their MoCA scores. To assess the role of neurogenesis in the association between CPSP and POCD, we can assess the correlation between changes in pain scores (and incidence of CPSP) with the MST, and separately with other cognitive/neuropsychological testing. According to the neurogenesis theory, as demonstrated in depressed patients recovering from their depressive state,¹⁷ we might see improved MST scores in patients who experience a postoperative improvement in their pain while still showing a postoperative decline in other cognitive domains/tests; and *vice versa*, patients with CPSP might show worsened MST scores, without showing significant changes in other cognitive tests/domains. Neurotrophic factors support the survival and function of hippocampal cells. Neurotrophic like the brain-derived neurotrophic factor (BDNF) and the insulin-like growth factor-1 (IGF-1) have been shown to enhance the association between higher aerobic fitness and better memory performance.²³ Conversely, a reduction in neurotrophic factors might mediate the interaction of pain, reduced mobility and satisfaction, with cognition (**objective 2.b**).

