2. OBJECTIVES

The overarching objective of the ArthroCaP study is to explore the interplay between postoperative pain and self-reported recovery (i.e. satisfaction), coping abilities/expectations about surgery, and postoperative COGNITIVE trajectories in ≥ 50 years old people undergoing elective total knee arthroplasty (TKA) or total hip arthroplasty (THA).

The specific objectives of the ArthroCaP study are:

1. to explore the association of CPSP, long-term opioid use, and a multi-domain measure of patient satisfaction, with POCD, measured as changes over time of the performance at the Montreal Cognitive Assessment (MoCA) score, and at additional neuropsychological testing.
2. to explore whether postoperative cognitive changes are associated with changes in neurogenesis correlates (a) and in neurotrophic factors levels (b), and whether this association is mediated by changes in pain, mobility, and satisfaction
3. to explore the association between coping strategies/expectations before and after surgery, as measured by the SPOC questionnaire, and cognitive changes after surgery; and to explore the correlation between changes in SPOC and cognitive changes from preoperative to 4-6 weeks after surgery.
4. to qualitatively explore lived experiences of pain, mobility and aging, including resilience, expectations and satisfaction with surgery, in patients undergoing TKA or THA across different ages and comorbidities.

The current protocol and ethics submission describes methods and seek ethics approval for specific objectives 1-3. Objective 4 will be covered in a separate protocol and ethics application.

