The classic MST consists of a series of 192 color photographs of everyday objects on a white background.²⁷ There are typically two phases: an incidental encoding phase, when participants engaged in an indoor/outdoor judgment for each picture (based on their opinion with no right or wrong answer); and a subsequent recognition test with a three-choice response. The objects include three stimulus types (each representing one third of the objects): exact repetitions of earlier items, lures that are similar but not identical to earlier items, and novel foils. During the test, participants are asked to identify each item as “Old,” “Similar,” or “New”. The recognition memory score is calculated as the difference between the rate of “Old” responses given to repeat items minus “Old” responses given to foils. The lure discrimination index (which measures mnemonic discrimination) is calculated as the difference between the rate of “Similar” responses given to the lure items minus “Similar” responses given to the foils. Typically, ‘normal’ aging is associated with a decline in mnemonic discrimination (i.e. (identifying lure objects that are similar to memory set objects as “similar”) with preserved recognition memory (identifying repeated memory set objects as “old”).²⁸ The traditional MST as here described has been used also in older people.^{29 30} It is available in a format for online administration. We are working with the task developers (<http://faculty.sites.uci.edu/starklab/mnemonic-similarity-task-mst/>) to have a validated modified online version of MST ready for use by the launch of our study; the modified version is adapted to increase the efficiency of the test (i.e. to obtain the same information but with a shorter test) and therefore its acceptability with older participants.²⁹

3) Additional neuropsychological testing

The following neuropsychological testing (available in electronic versions for online administration) will be additionally performed:

- the Visual Paired Associates Learning (PAL) test, designed after the Cambridge Neuropsychological Test Automated Battery (CANTAB) – PAL test, which measures hippocampal-dependent visuo-spatial memory by testing participant’s memory for object location pairs. For this test (expected time requirement 10 minutes), boxes are

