3.6 Statistical analyses

Baseline characteristics will be summarized through descriptive statistics, i.e. mean (standard deviation), median (interquartile range [IQR]), or number (%) as appropriate.

Objective 1. We will first evaluate the primary study objective modeling longitudinal changes in pain scores (independent variable) and changes in cognitive/neuropsychological scores (dependent variable) over time (4 weeks, and 3, 6, and 12 months after surgery) using multilevel (mixed effects) regression models, considering time points nested within patients.³⁶ Secondly, in mixed effects models, we will specifically look at whether experiencing moderate-severe persistent pain at 3 months after surgery (or at 6 months after surgery) predicts subsequent decline in cognitive performance (i.e. at 6 and 12 months, or at 12 months).⁹ Models will be adjusted for relevant covariates, including baseline characteristics (at the patient level, e.g. age, sex, comorbidity index, and anxiety/depression level) and pain medications as time-varying variables. We will adopt a parsimonious approach in covariates selection, based on clinical relevance and removing collinear covariates (i.e., variance inflation factor > 2.5) according to pre-specified priorities. We will use the same statistical approach to look at the association between satisfaction (measured with the SAPS instrument) and cognitive performance.

Objectives 2. We will explore our objective 2a, analyzing separately change in MST scores and changes in other cognitive performance measures. Bonferroni correction of alpha values will be adopted to adjust for multiple comparisons. For the biomarker study (objective 2b), we will similarly model mixed effects regression models to evaluate how the biomarker levels change over time and how these changes correlate with changes in pain, satisfaction, and cognitive performance. We will also analyze whether biomarkers levels at baseline (before surgery), and

right after surgery (or at 4-6 weeks after surgery) predict cognitive changes/decline at 6 and 12 months.

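### Does objective 2a need a direct contrast between the MST and the other cognitive tests?

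*Combined protocol and SAP*

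**What the plan says.** The Background gives the idea behind objective 2a: "One interesting hypothesis is that pain and satisfaction might interact with cognitive abilities through neurogenesis interference". It then says how this would be examined: "To assess the role of neurogenesis in the association between CPSP and POCD, we can assess the correlation between changes in pain scores" (and in CPSP incidence) "with the MST, and separately with other cognitive/neuropsychological testing". Two patterns are offered as things the investigators might see. In patients whose pain improves, MST scores may rise "while still showing a postoperative decline in other cognitive domains/tests". Conversely, "patients with CPSP might show worsened MST scores, without showing significant changes in other cognitive tests/domains".

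Section 2 states the formal objective: "to explore whether postoperative cognitive changes are associated with changes in neurogenesis correlates" and in neurotrophic factors, and whether pain, mobility and satisfaction mediate this.

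Section 3.6 plans, for 2a, "analyzing separately change in MST scores and changes in other cognitive performance measures", with a Bonferroni adjustment. It states no joint model, no difference between tests, and no rule for declaring that the tests behave differently. Section 3.5 calls the study proof-of-concept and exploratory, and sets the target at 100 patients.

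**The concern.** The Background's prediction is about a difference: pain should go with the MST and not, or not in the same way, with the other tests. Separate analyses give separate coefficients and p-values. If the MST result is significant and the others are not, that alone does not show that the associations differ, because the others may simply have missed the threshold. Bonferroni makes missing it easier, and under the CPSP prediction a miss counts in favour of the hypothesis.

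At stake would be how strongly a neurogenesis mechanism is carried into later studies. All the tests share the same visits in Appendix I, so a contrast would need no new data, which makes its absence look like an oversight.

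**Working it through.** **1. Text against text.** The Background proposes correlations with the MST and, separately, with the other tests; section 3.6 does that. Section 2 asks about association and mediation, and an MST-minus-others contrast answers neither. The dissociation appears only as a possible finding in the Background. So the plan neither contradicts its rationale nor commits to the faulty inference.

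**2. How often would the described pattern mislead?** The plan has no figure for 2a to reproduce; the only power statement, in section 3.5, concerns objective 1.

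Inputs from the documents: n = 100 and 30% with moderate-severe CPSP (section 3.5); six tests, namely MST, MoCA, PAL, RVP, N-back and Stroop (section 3.4.1); Bonferroni (section 3.6).

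Assumptions: a divisor of six, so alpha = 0.05/6 = 0.0083, two-sided; inter-test correlation 0.3–0.5; the effect sizes shown. Each setting used 20,000 simulated studies with no true dissociation. The pattern is MST significant and all five others not. The contrast is MST minus the mean of the other five, tested at 0.05.

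| Setting | Pattern occurs | Contrast rejects, change-SD units | Contrast rejects, baseline-SD units |
|---|---|---|---|
| Equal correlation with pain change, 0.20 | 3.9–4.7% | 2.6–4.5% (over 0.2–0.4) | 8–22% (over 0.2–0.4) |
| Same, 0.30 | 1.0–1.3% | as above | as above |
| Same, 0.40 | about 0% | as above | as above |
| CPSP (30) versus none (70) | 2.0–4.5% (0.4–0.6 SD) | 3.2–4.5% (0.4–0.8 SD) | 8–19% (0.4–0.8 SD) |
| Change within 30 CPSP patients, 0.3–0.6 SD | 0.9–4.6% | – | – |
| Reliability 0.8 (MST) and 0.5 (others), true correlation 0.2–0.4 | 2–9% | 6–15% | – |

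The pattern is rare because five tests must all miss at once.

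**3. Why the contrast's error rate moves.** Suppose every test has the same correlation r with pain change, and the SD of change, in baseline-SD units, is 1.0 for the MST and 0.77 for the others (assumed). In change-SD units the slope difference is r − r = 0. In baseline-SD units it is r × (1.0 − 0.77) = 0.23r, which is 0.069 at r = 0.30. The same data therefore satisfy the null on one scale and violate it on the other. Reliability acts likewise: a true correlation of 0.30 is observed as 0.30 × √0.8 = 0.268 for the MST and 0.30 × √0.5 = 0.212 for the others, a gap of 0.056 with no dissociation. The documents give neither the variances nor the reliabilities.

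**4. What the contrast would deliver.** With five comparators and inter-test correlation r, its variance in change-SD units is 1 + (1 + 4r)/5 − 2r. This is 0.84 at r = 0.3 (SD 0.917) and 0.60 at r = 0.5 (SD 0.775).
- Pain change: the 95% half-width is 1.984 × 0.917/√98 = 0.18 and 1.984 × 0.775/√98 = 0.16.
- CPSP: √(1/30 + 1/70) = 0.218, giving 1.984 × 0.917 × 0.218 = 0.40 and 1.984 × 0.775 × 0.218 = 0.34.

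These assume one change score per patient, complete data and no covariates.

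**5. What it would require.** "The lure discrimination index (which measures mnemonic discrimination) is calculated as the difference", but the MST also yields a recognition score, so an index must be chosen. Section 3.4.1 names no summary score for PAL, RVP, N-back or Stroop, and it describes PAL as hippocampal-dependent, so whether PAL belongs in the comparator is arguable. Two exposures, with and without PAL, under two scalings make 2 × 2 × 2 = 8 estimates, so this is more than one additional line of analysis.

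**The case for a change.** The strongest case for the concern does not rest on error rates. The mechanism turns on a difference, and the plan will not report that difference with a confidence interval. This is true. The separate coefficients can be compared by eye, but without a measure of uncertainty. If a dissociation is real (correlation 0.3 for the MST, 0 for the others), the contrast detects it in 92–98% of simulated studies, while the significance pattern appears in about 64%. That advantage also stands.

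Larger rates of misleading results can be produced. Two tests with equal true associations disagree on significance in 8–40% of studies. But that counts disagreement in either direction between only two tests, and the upper end uses an unadjusted 0.05. MST significant with MoCA not occurs in 9–21% at mid-range effects. The Background describes neither: it speaks of the other tests and domains together. Someone who later picked out a single non-significant test would be misreading the results, but the plan does not propose this.

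The point about significance versus difference also does not touch the Background's other prediction, in which the MST improves while other tests decline.

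**Conclusion.** The concern does not hold. Section 3.6 carries out what the Background proposes, the formal objective is worded as association and mediation, and no stated rule turns separate p-values into a claim of dissociation; nor is a later comparison excluded. The pattern that could mislead arises in about 0–5% of studies when the tests are equally related to pain, and in 2–9% if the MST is the more reliable measure. That is broadly no worse than the contrast, at about 3–5%, 8–22% or 6–15% depending on scale and reliability.

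These figures rest on assumed effect sizes, inter-test correlations of 0.3–0.5, a divisor of six and 100 complete patients. The textual argument needs none of them. An exploratory contrast would be a reasonable extra with better power for a true dissociation, but its scale, index and comparator are open to debate. In a study that describes its own results as preliminary, omitting it is a choice of analysis and needs no correction.

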APPENDIX I summarizes the timeline, measurements, and data collection for the ArthroCaP study. The baseline and longitudinal assessments will occur in compliance with the local restrictions to research due to the COVID-19 pandemic and based on patient acceptance. Patient surveys will be completed over the phone or via videoconference. For cognitive/neuropsychological testing, the study will employ tools that are validated for remote administration, including online/electronic versions or versions adapted for administration through videoconference by trained personnel. For the baseline and every postoperative longitudinal assessment, patients will be invited to schedule a videoconference with the research personnel who will administer the tests or supervise the self-administration of the tests, depending on the specific test as described in 3.4.1. In case of change of the regulation currently in force, in-person assessments following the same timeline will be considered and offered to the participants as an option. Likewise, whenever the participant is due for clinical reasons for an in-person visit, which is occurring in agreement with the study timeline, the option of performing the study assessments during the in-clinic visit will be offered to the participant. If necessary, the participants will be allowed to involve in the study a next of kin or support person who can help facilitate the access to an electronic device with an internet connection which will be used for the study videoconferences and for the administration of the online web-based neuropsychological tests. The videoconference-based assessments will be conducted using any of the following software options which allow screen sharing, i.e., McMaster Zoom, Microsoft Teams or Webex, based on availability and participant discretion. We expect each study videoconference/visit for the cognitive/neuropsychological assessment to last between 45 and 60 minutes.

Blood drawing will occur based on the study timeline (**APPENDIX I**) and in agreement with research restrictions in force (see 3.4.2).

We will seek patient confirmation of consent to participate in the study at every in-person or virtual visit throughout the study.

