displayed on the screen and are opened in a randomized order. One or more of them will contain a pattern. The patterns are then displayed in the middle of the screen, one at a time, and the participant must touch the box where the pattern was originally located. If the participant makes an error, the patterns are re-presented to remind the participant of their locations. The difficulty level increases through the test;

- the Rapid serial Visual Presentation (RVP) test (designed after the CANTAB-RVP test), which assesses executive function (working memory and sustained attention). For this test (expected time requirement 7-10 minutes), a white box is shown in the centre of the screen, inside which digits from 2 to 9 appear in a pseudo-random order, at the rate of 100 digits per minute. Participants are requested to detect target sequences of digits (for example, 2-4-6, 3-5-7, 4-6-8). When the participant sees the target sequence they must respond by selecting the button in the centre of the screen as quickly as possible. The level of difficulty varies with either one- or three-target sequences that the participant must watch for at the same time.
- the N-back test, which assesses visual working memory. For this task (expected time requirement 7-10 minutes), participants are shown a series of numbers on the screen, and are occasionally asked to enter the number they saw 2 numbers ago; AND
- the Stroop word colour interference task, which assesses inhibitory control. For this test (expected time requirement 5-10 minutes), participants will be tested on their ability to identify the color of the word, not what the word actually states. This acts as a test of attention by tapping the ability to suppress a habitual response in favor of a less familiar one, and provides additional indices of simple attention like word reading and color identification.

4) Subjective Memory Complaints (SMC)

We will also assess Subjective Memory Complaints (SMC).³¹ Participants will be asked the following 4 questions: i) “Do you have any difficulty with your memory?” ii) “Do you forget where you have left things more than you used to?” iii) “Do you forget the names of close friends or relatives?” and iv) “Do other people find you forgetful?”. A positive response to any of these questions will indicate SMC.^{32 33}

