Objective 3. To evaluate the role of coping abilities and expectations, as measured by the SPOC questionnaire, we will first analyze the association between baseline SPOC and baseline cognitive performance in a traditional multivariable linear regression analysis; similarly, we will analyze the association between early postoperative (4-6 weeks) SPOC and cognitive performance, after adjusting for baseline measurements. Then we will analyze whether preoperative and postoperative SPOC predict cognitive decline at 6 and 12 months using linear and logistic (i.e. with ≥ 2 point decline in MoCA as binary outcome) regression models.

All the analyses for all the objectives will be first conducted in the overall sample of study participants. As additional analysis, we will explore whether there is a signal for any subgroup effect based on the type of surgery performed, i.e., knee versus hip arthroplasty. We will undertake such exploratory subgroup analyses as long as both subpopulations reach at least 30% of representation.

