APPENDIX I. Study timeline, measurements, and data collection

Measurement	Before surgery		Day of surgery (2-4 hours after surgery)	After surgery			
	Day -28 to -1	Day of surgery		+4-6 weeks	+3 mo	+6 mo	+12 mo
	Online - Videoconference with research team or in person	In person	In person	Online - Videoconference with research team or In person			
Socio-demographics	x						
Comorbidities/ Medical History	X						
Surgical characteristics				x			
Pain Medication Usage	x			x	x	x	x
The Somatic Preoccupation and Coping (SPOC) Questionnaire	x			x			
FRAIL Scale (Frailty assessment)	X						
Hospital Anxiety and Depression Scale (HADS)	X						
Pain Assessment	x			x	x	x	x
Self-Administered Patient Satisfaction (SAPS) Scale					x	x	x
Complications				x	x	x	x
Cognitive/ neuropsychological assessment - MoCA - MST	x			x		x	x

- Other neuropsychological testing - SMC							
Blood drawing for biomarker study		x	x*	x**		x**	x**

*the subset of patients that stay in hospital at least one night after surgery will have blood collected also every morning on postoperative day 1-3, or until discharge (whichever comes first)

**whenever an in person study visit is feasible depending on restrictions in place due to the pandemic and patient compliance
MoCA, Montreal Cognitive Assessment; MST, Mnemonic Similarity Task; SMC, Subjective Memory Complaints

REFERENCES

4. Neuro VI. Perioperative covert stroke in patients undergoing non-cardiac surgery (NeuroVISION): a prospective cohort study. *Lancet* 2019;394(10203):1022-29. doi: 10.1016/S0140-6736(19)31795-7

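### Objective 3 uses single-visit regressions at 6 and 12 months with no method for missing scores, so MoCA scores already collected go unused; this costs precision and can bias the SPOC result

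*Combined protocol and SAP*

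**What the plan says.** For Objective 3, section 3.6 asks whether SPOC before and after surgery will predict "cognitive decline at 6 and 12 months using linear and logistic (i.e. with ≥ 2 point decline in MoCA as binary outcome". Each of these models has one outcome, taken at one visit.

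For Objective 1, the same section models the repeated scores "using multilevel (mixed effects) regression models, considering time points nested within patients".

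On who is analysed, it says only "All the analyses for all the objectives will be first conducted in the overall sample of study participants". That sentence introduces the knee and hip subgroups and is not a rule for missing outcomes. The plan contains no missing-data method, no dropout allowance and no rule for a participant who stops the cognitive sessions.

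Appendix I schedules the cognitive battery (row "Cognitive/ neuropsychological assessment - MoCA - MST") at baseline, 4-6 weeks, 6 months and 12 months. Section 3.3 expects each session to take 45-60 minutes and adds: "We will seek patient confirmation of consent to participate in the study at every in-person or virtual visit throughout the study".

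**The concern.** Someone tested at baseline, 4-6 weeks and 6 months but not at 12 months has two postoperative MoCA scores. Both say something about the missing third, yet the 12-month linear and logistic models as named can use neither. The same holds at 6 months for someone last tested at 4-6 weeks.

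Loss need not be random. The outcome is cognitive decline, the exposure is coping, and the sessions are long, device-based cognitive tests. Section 1 itself suggests that coping and cognition may affect each other. If those who have declined and those who cope poorly both leave more often, the people left are a selected group, and the SPOC coefficient estimated in them is shifted.

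The study is meant to inform larger confirmatory work (sections 3.5 and 4), so a shifted association, or a shifted decline frequency in the analysed group, could be carried into the next design.

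**Working it through.** The plan gives no power or precision figure for Objective 3, so there is none to reproduce. The power statement in section 3.5 concerns pain (Objective 1) and a superseded sample size, and does not bear on this point.

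**Inputs from the documents.** Target 100 patients and 20% with a decline of at least 2 MoCA points at 1 year (section 3.5); visit schedule (Appendix I). The only retention figure is at least 80% for 12-month blood samples (section 3.4.2), which does not concern cognitive testing.

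**Assumed, because the documents are silent.** Loss of 10% or 20% at 12 months; SD of MoCA change 2.3; correlation 0.6 between the 6- and 12-month residuals; SPOC slope -0.60 MoCA points per SD (higher = worse coping); and the dropout mechanisms below.

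**Step 1: events.**
- Expected decliners: 100 × 0.20 = 20.
- Random 20% loss: 20 × 0.80 = 16 decliners among 80, still 20%.
- Decliners twice as likely to be lost: solve 80r + 20(2r) = 20, so r = 1/6. Decliners left: 20 × (1 - 2/6) = 13.3, and 13.3/80 = 16.7%.

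**Step 2: size of bias.** 600,000 simulated participants, with change at 6 and 12 months = -0.60·z + error, shifted so that 20% decline by at least 2 points at 12 months. Dropout: logit = a - g·(6-month change) + h·z, with a set to give 20% loss.

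| Dropout depends on | g | Complete-case decline | Slope | Slope too small by |
|---|---|---|---|---|
| 6-month change only (h = 0) | 0.15 | 18.7% | -0.596 | 1% |
| | 0.3 | 17.5% | -0.579 | 4% |
| | 0.5 | 16.1% | -0.554 | 8% |
| 6-month change and SPOC (h = 0.5) | 0.15 | 18.1% | -0.566 | 6% |
| | 0.3 | 16.9% | -0.526 | 12% |
| | 0.5 | 15.6% | -0.485 | 19% |

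The last column is 1 - slope/(-0.60). At 10% loss with h = 0.5, decline is about 17.5-19.0% and the slope is about 4-12% too small. Imputing from the 6-month score and SPOC returns 20% and about -0.60 in every row.

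**Step 3: other mechanisms.** A second simulation (400,000 participants, true decline 19.2%, 20% loss) also fitted the logistic model. Slope and log OR are given as a share of the truth.

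| Dropout depends on | Complete-case decline | Slope | Log OR |
|---|---|---|---|
| SPOC alone | 18.1% | unbiased | unbiased |
| 6-month change alone | 17.1% | 98% | 99% |
| 12-month decline alone | 15.2% | 94% | 99% |
| Not having declined | 21.8% | 103% | 100% |
| 6-month change and SPOC | 16.2% | 90% | 91% |
| Unseen 12-month decline and SPOC | 14.2% | 86% | 76% |

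Completely random loss gives no bias. Using the earlier scores restores the fifth row fully (19.2%, slope -0.605 against -0.602). It restores the sixth only in part (16.1%, slope 90%, log OR 87%).

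**Step 4: gain at the planned size.** In simulated studies of 100 (g = 0.3, h = 0.5, 20% loss), the root mean squared error of the slope was 0.277 with complete cases and 0.259 with imputation: 0.259/0.277 = 0.935, about 6-7% smaller.

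**The case against.** **The bias is small against noise.** With 80 analysed, the slope's standard error is about 2.3/√80 = 0.26, against a bias of 0.034 to 0.115 (0.60 less the h = 0.5 slopes). For the decline rate it is √(0.2 × 0.8/80) = 4.5 points, against 1.9 to 4.4. The study calls itself exploratory. This stands, and it limits the weight of the point. It does not favour complete cases, which do slightly worse even at this size.

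**Complete-case analysis is inferred.** True: the plan never says so. But it names models that need the visit's outcome and offers no alternative.

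**Objective 1 has a similar weak spot.** Its test of 6-month pain against 12-month decline also has a single later outcome. That is fair, so the contrast rests on Objective 1's main longitudinal model.

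**The plan eases testing.** Section 3.3 offers in-person sessions at clinic visits and a support person to help with the device. These should reduce loss but do not say how the remaining loss is analysed.

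**Stronger readings that the documents do not support.**
- A reader might infer that the plan will understate decline and weaken the SPOC association. No dropout rate or mechanism is given; several mechanisms leave the association almost untouched, and one reverses the error.
- A reader might infer that whoever stops leaves all of Objective 3. They leave only the model at the missed visit.
- A reader might infer that telephone contact could rescue the outcome, since "Patient surveys will be completed over the phone or via videoconference". Section 3.4.1 specifies the remote MoCA by audio-visual conference, so a call cannot supply it as planned.
- A reader might infer that the memory-complaint questions ("A positive response to any of these questions will indicate SMC") are lost with the session because Appendix I lists them together. Nothing bars asking them by phone, and Objective 3 does not name them as an outcome.

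**Conclusion.** The point holds as an inexpensive improvement to the analysis. As written, Objective 3 cannot use postoperative scores that the study collects, and the plan gives no rule for missing ones. Lower precision follows from any loss. Bias is possible but conditional: a material attenuation of the SPOC association needs loss tied to both SPOC and decline.

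The sizes found in the working rest on assumed values for the loss, the SD, the correlation, the SPOC slope and the dropout mechanism. They show what could happen and do not forecast this study. The case for change rests on the better use of data already in hand, and does not require any one of those mechanisms to be true.

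**What to change.** In section 3.6, Objective 3:

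1. Take the 6- and 12-month SPOC contrasts from a mixed model using all visits. Alternatively, multiply impute missing 6- and 12-month MoCA from baseline and all available postoperative cognitive scores, SPOC, pain and HADS. For the logistic model, derive the decline of at least 2 points from the imputed score.
2. Show complete cases as a sensitivity analysis and report the number analysed at each visit.
3. Record the reason for each missed cognitive session.
4. Add a delta-type sensitivity analysis in which imputed scores are shifted downward over a stated range.

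Cost: a short change to the analysis text, one field on the case report form and some programming. No extra visits or staff. Downside: items under 1 assume that missingness is explained by the observed data. If loss depends on the unseen 12-month score, they recover only part of the bias, which is why item 4 is needed.
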